For these analyses, we will use Poisson regression where the outcome is the number of patients with any AP order. The offset is the number of patients at risk. For this secondary analysis, treatment arm will be the only covariate included in the regression model, and the estimated coefficient is interpreted as the log-RR of number of patients with AP order from an intervention provider vs. a control provider. Provider will be the unit of analysis for this regression model, and the regression model will be fit using generalized linear model (GLM). We will construct a 95% confidence interval (CI) around the estimated RR. Our null hypothesis is that the RR is equal to 1, corresponding to no statistically significant difference between the number of patients with AP orders from treatment and control providers. If the upper bound of the 95% CI is below 1, we will reject the null hypothesis and conclude that the RR of prescribing AP to an “at risk” patient, is lower from the intervention vs. control providers, with a starting point after exposure to the BPA, until the end of the study enrollment (and vice-versa for a 95% CI above 1).

Sustainment Analysis:

Descriptive analysis will summarize the outcome distribution across providers. Within a provider, the outcome is **the percent of eligible patients with any AP order after July 1st 2020, with an ending time on December 31st 2020** i.e., the first time the Control BPA is fired for both the Intervention and Control arms. (Note that July 1st, 2020 – December 31st, 2020 is defined as the post period, while time on study i.e. before July 1st 2020, is defined as the pre period). After the first BPA firing, AP order will be recorded starting from the “at risk” patient seen by the providers up until December 31st, 2020. Note that most patients in the denominator for this outcome (at-risk patients) will not have an AP order and, thus, will not be enrolled in the study. “At risk” patients are defined as patients who meet eligibility criteria for the study i.e. patients who have the 13 diagnoses used for eligibility or the study, and do not have exclusion diagnoses (psychosis, mania, autism, developmental disability) or recent AP exposure used for ineligibility. The numerator and denominator for this outcome are patient counts: number of at-risk patients with any AP order/ number of at-risk patients, stratified by pre and post periods. Some at-risk patients may be seen multiple times by the provider, but they only contribute once to the numerator (any AP order, 0 or 1), and they only contribute one at-risk patient to the denominator. The numerator for each provider will be equal to the number of patients enrolled by that provider in the study.

Inferential analysis will estimate the **relative risk (RR) of prescribing an AP to an at-risk patient by intervention providers versus control providers after first exposure to study.**

For this analysis, we will use Poisson regression where the outcome is the number of patients with any AP order after July 1st, 2020. For this secondary analysis, treatment arm will be the only covariate included in the regression model, and the estimated coefficient is interpreted as the log-RR of number of patients with AP order from an intervention provider vs. a control provider. Provider will be the unit of analysis for this regression model and the regression model will be fit using generalized estimating equations (GEE) to account for correlation within provider. We will estimate standard errors using a robust (sandwich) covariance estimation (assuming a working independence covariance structure) and construct a 95% confidence interval (CI) around the estimated RR. An interaction term between treatment and the time period (pre versus post) will give us the estimates. Our null hypothesis is that the RR is equal to 1, corresponding to no statistically significant difference between AP order rates in treatment vs. control patients in the post period. If the upper bound of the 95% CI is below 1, we will reject the null hypothesis and

Analysis plan for Safety Use of Antipsychotics in Youth (SUAY)

conclude that the RR of AP use is lower for intervention vs. control patients in the post period (and vice-versa for a 95% CI above 1).

Variables	Definition	Present/Absent
pid	provider type based on specialty	present
groupn	Randomization Group - use for descriptive stats (Intervention (1)/Control(2))	present
group_cat	Randomization Group - use in models (Control (0)/Intervention (1))	present
provider_type	This is the total number of eligible patients with at least one AP order, seen by each provider, starting from July 1st 2020 to December 31st 2020	present
n_pt_pre	The total number of "at-risk" patients that would have been enrolled in the study if the provider would have prescribed AP, before July 1 st 2020	variable absent, value absent
n_pt_post	The total number of "at-risk" patients that would have been enrolled in the study if the provider would have prescribed AP, starting from July 1st 2020 to December 31st 2020	variable absent, value absent
pre_offset	The total number of "at-risk" patients that would have been enrolled in the study if the provider would have prescribed AP, before July 1st 2020	variable absent, value absent
post_offset	This is the total number of eligible patients with at least one AP order, seen by each provider, before July 1st 2020	variable absent, value absent

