All primary analyses will follow an intent-to-treat approach, including all individuals assigned to an intervention arm regardless of the amount of intervention received. Non-inferiority evaluations will also be evaluated in a supplementary “as treated” analysis, comparing outcomes according to treatments actually received by patients during their observed period of follow-up. This supplemental comparison is useful in a non-inferiority assessment due to the fact that the alternative hypothesis of “no effect” is more likely in the presence of protocol violations and therefore the intent to treat approach will be anti-

conservative if many patients in the intervention arm, for example, revert to control. Also, non-inferiority of Emergency Department visit rate in the intervention arm compared to usual care control will only be assessed on final analysis if superiority is shown for the primary endpoint of no antipsychotic use at 6 months.

We will use Poisson regression to estimate (1) the percent of individuals using antipsychotics at 6 months post enrollment and (2) the total number of person-months of antipsychotic use by youth in the six month follow-up period, per provider medication orders, in each of the study arms. We will use generalized estimating equations(43) to estimate the parameters in the Poisson regression model. We will use the robust sandwich estimator to ensure correct standard errors for the intervention effect due to possible violation of the Poisson variance assumption(44); additionally, this will allow us to account for any clustering within clinics(43) and providers. Poisson regression allows comparison of relative incident rates among the intervention arms when outcomes are not rare(45). Additionally, Poisson regression will allow us to control for pre-specified baseline covariates (age, gender, and race) as well as site differences in any antipsychotic use and allow for straightforward estimation of site-specific intervention effects in sensitivity analyses. For a secondary analysis, we will repeat this approach defining antipsychotic use with prescription fill data rather than orders.

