divided by the rate on control, estimated by Poisson regression) and 95% two-sided confidence interval (CI) will be compared to the non-inferiority margin (overall: $M = 1.5$) and non-inferiority of the algorithm approach will be declared if the entire coverage of the 95% CI is less than 1.5.

In safety review reports, the ratio between arms of emergency department visit rates will be accompanied by a confidence interval and by the non-inferiority margin, 1.5, for reference. Confidence intervals will be defined by estimating the rate ratio in 5,000 bootstrap samples. Resampling will be done on the cluster (provider) level and stratified by the presence of any event within each cluster. Quantile-based confidence intervals will be identified using the appropriate percentile corresponding to the Pocock alpha-spending function for interim analyses. Excess harm is observed if the entire coverage of the confidence interval for the rate ratio comparing the greater to the lesser rate of emergency department and urgent care visits is greater than 1.5. (While the final non-inferiority analysis for this safety outcome will use the robust sandwich estimator to ensure correct standard errors, the properties of this estimator are based on asymptotic behavior and small sample size performance may be poor.)

We anticipate initial follow-up of 800 patients, randomized to the two arms, with 720 patients remaining enrolled in the study at 6 months of follow-up (i.e., 10% lost to follow-up). Assuming a $P < 0.05$ alpha level, and based on an anticipated 95% of patients in the control arm using antipsychotics at 6 months, this sample will ensure over 95% power to detect a 6% reduction in the percent of participants with any order for antipsychotic medications at 6 months. Furthermore, we expect to have 80% power to detect a 13% reduction in subgroups with exposures occurring with 25% prevalence, and 80% power to detect a 17% reduction in subgroups with exposures occurring with 18% prevalence (e.g., racial/ethnic minorities). A minimal clinically important difference of 10% was pre-specified to allow for evaluation of clinical significance as well as statistical significance. We have over 90% power to detect a 10% reduction in antipsychotic use at 6 months for patients in the intervention arm given a rate of 85%, 90%, or 95% use in the control arm.

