Patient enrollment in the study occurs when a provider writes a qualifying antipsychotic prescription for an eligible adolescent patient or enters a patient reported medication (these two actions are indistinguishable in Epic). (Eligibility is confirmed by study staff following enrollment.) Follow-up time after enrollment extends for 6 months (181 days). Some patients will not remain enrolled in the health plan for a full six months, censoring follow-up, and the number of days covered in the health plan post-study enrollment should be recorded. If patients have a health care plan enrollment gap that is less than 45 days, they will be considered as having continuous enrollment in the study (i.e. not loss to follow up). For example, if a patient has a gap in their healthcare plan enrollment for less than 45 days during the study, this patient will be considered to have continuous enrollment. However, if there is an enrollment gap in their healthcare plan for at least 45 days, the patient will be disenrolled from the study at the healthcare plan disenrollment day. Note that, since patients do not have to be enrolled with a specific health care plan to be seen at NCH, we will assume a full follow up time of 6 months (181 days). Follow-up time should be indicated in the analytic dataset for all enrolled patients.

Analysis

Primary analysis I

Our primary analysis examines the percentage of patients taking antipsychotic medications (measured by provider medication orders) at 6 months post enrollment

Descriptive analysis will summarize **the percent of patients observed to be using AP at 6 months**, defined by presence of days' supply AP ≥ 181 days or medication in hand at 6 months. For example, if a patient has a 30-day supply order on or after 151 days post-enrollment, that patient has AP medication "in hand" at 6 months. Note: a patient does not have to have ≥ 181 days' total supply during the study to have medication in hand at 6 months. We will not adjust for loss to follow-up or disenrollment for this outcome definition. Patients who do not have prescription fill information up to 6 months post-baseline due to health plan disenrollment will have AP use observed at 6 months if they have AP orders after disenrollment that is ≥ 181 days. For example, if a patient disenrolls at day 160 and has a AP order (30 days' supply) after disenrollment, they have medication "in hand" at 6 months

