Inferential analysis for this outcome will estimate **the odds ratio (OR) of AP use observed at 6 months** between intervention and control. For this analysis, we will use a logistic regression model where the outcome is a binary indicator of AP use observed at 6 months. Binary treatment arm assignment and any inpatient hospitalization in the prior year will be the only covariates

Analysis plan for Safety Use of Antipsychotics in Youth (SUAY)

included in the regression model. The estimated coefficient associated with treatment is interpreted as the log-OR of observing AP use at six months for an intervention patient vs. a control patient. Patient is the unit of analysis, GEE will be used to account for correlation within provider, and robust standard errors (with working independence covariance matrix assumed) will be calculated to construct a 95% CI around the estimated OR. Our null hypothesis is that the OR is equal to 1, corresponding to no statistically significant difference between AP use observed at 6 months. We will reject the null hypothesis if the lower bound of the 95% CI is above 1 (increased use in treatment arm) or the upper bound is below 1 (decreased use in treatment arm).

Variables	Definition	Present/Absent
taking_at_6mon	Using AP at 6 months (No (0)/Yes(1))	present
groupn	Randomization Group - use for descriptive stats (Intervention (1)/Control(2))	present
group_cat	Randomization Group - use in models (Control (0)/Intervention (1))	present
prior_hosp	Prior Hospitalization (No (0)/Yes(1))	present

Sensitivity analysis will be conducted using similar approach as mentioned above, we will perform the following separate analyses related to our primary outcome by:

- % of patients taking antipsychotic medications (measured by orders) at 6 months post enrollment, using the minimum based on SIG reviews
- % of patients taking antipsychotic medications (measured by orders) at 6 months post enrollment, using the maximum based on SIG reviews
- % of patients taking antipsychotic medications (measured by prescription fills) at 6 months post enrollment. Note that this analysis may be performed using three healthcare systems (KPWA, KPCO, and KPNW) due to limitation in data availability

Variables	Definition	Present/Absent
taking_at_6mon_min	Using AP at 6 months - minimum (No (0)/Yes(1))	present
taking_at_6mon_max	Using AP at 6 months - maximum (No (0)/Yes(1))	present
taking_at_6mon_fills	Using AP (fills) at 6 months (No (0)/Yes(1))	present

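### Primary analysis I plans a confidence interval only for an odds ratio, so the protocol's 10% minimal clinically important difference has no interval to be read against

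*SAP*

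**What the plan says.** **SAP, Primary analysis I.** The descriptive part summarises "the percent of patients observed to be using AP at 6 months", and the variable list includes an arm indicator for descriptive statistics, so percentages by arm are planned. The inferential part estimates "the odds ratio (OR) of AP use observed at 6 months" from a logistic model with arm and prior-year hospitalization as the only covariates, fitted by GEE with provider as the cluster. Robust standard errors "will be calculated to construct a 95% CI around the estimated OR", and the null hypothesis is rejected when that interval excludes 1. The sensitivity and subgroup analyses follow the same approach. The SAP does not mention the minimal clinically important difference and gives no reason for leaving the protocol's model. Primary analysis II keeps Poisson regression and a relative risk.

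**Protocol 8.2.1.** The planned model for this outcome was Poisson regression by GEE with robust standard errors, on the ground that "Poisson regression allows comparison of relative incident rates among the intervention arms when outcomes are not rare". On effect size it says: "A minimal clinically important difference of 10% was pre-specified to allow for evaluation of clinical significance as well as statistical significance". The power statement is "based on an anticipated 95% of patients in the control arm using antipsychotics at 6 months", with 90% and 85% as alternatives. The power table lists percentages in each arm at 360 patients per arm.

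**The concern.** The protocol states its clinical criterion on the percentage scale. The SAP's only estimate with an interval for this outcome is on the odds scale. When most patients have the outcome, the relation between the two scales depends strongly on the control percentage, so one OR can stand for a reduction below, at or above 10 points. The planned OR is also conditional on prior hospitalization. Odds ratios are non-collapsible, so combining the adjusted OR with crude arm percentages does not give an exact marginal difference or its interval.

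At stake is the judgement of clinical significance for which the protocol set the criterion. A reader would have a crude difference with no interval and an OR interval that cannot be set against 10 points. The trial could then say whether use differed, but not whether the data support or exclude a difference of the size declared important.

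**Working it through.** **Inputs.** 360 evaluable patients per arm (protocol 8.1 and power table). Control use of 95% anticipated, 90% and 85% as alternatives (protocol 8.2.1). Minimal important difference of 10%, scale not named. Alpha 0.05, taken as two-sided.

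**Step 1: which scale is the 10%?** Power for two proportions with pooled variance under the null is Φ{(|p0 − p1| − 1.96·√[2p̄(1 − p̄)/n]) / √[p0(1 − p0)/n + p1(1 − p1)/n]}, where p̄ = (p0 + p1)/2 and n = 360. For 80% v 90%: (0.10 − 1.96 × 0.0266)/0.0264 = 1.815, giving 96.5%.

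| Control | 10 absolute points | Protocol table | 10% relative |
|---|---|---|---|
| 95% | 99.5% | >99% | 99.1% |
| 90% | 96.5% | 97% | 93.1% |
| 85% | 92.0% | 92% | 82.6% |

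Absolute points reproduce all three rows. A relative 10% falls short of the protocol's claim of more than 90% power at 85% control use. The figures therefore support 10 absolute points.

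**Step 2: ten points as OR and RR.** OR = [p1/(1 − p1)]/[p0/(1 − p0)]; RR = p1/p0.

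| Control p0 | Intervention p1 | OR | RR |
|---|---|---|---|
| 0.95 | 0.85 | (0.85/0.15)/(0.95/0.05) = 0.298 | 0.895 |
| 0.90 | 0.80 | (0.80/0.20)/(0.90/0.10) = 0.444 | 0.889 |
| 0.85 | 0.75 | (0.75/0.25)/(0.85/0.15) = 0.529 | 0.882 |

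**Step 3: a fixed OR as percentage points.** With o = OR × p0/(1 − p0), p1 = o/(1 + o) and the reduction is p0 − p1.

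| OR | Control 95% | Control 90% | Control 85% |
|---|---|---|---|
| 0.298 | 10.0 | 17.2 | 22.2 |
| 0.444 | 5.6 | 10.0 | 13.4 |
| 0.529 | 4.0 | 7.4 | 10.0 |

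Within the protocol's own scenarios, the same OR can miss, meet or exceed the criterion.

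**Step 4: does the conclusion need the absolute reading?** No. A relative 10% reduction is RR 0.90 throughout, but OR 0.310, 0.474 and 0.574 at 95%, 90% and 85%.

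**Step 5: why a point difference is not enough.** The approximate 95% half-width for a 10-point difference is 1.96·√[p0(1 − p0)/360 + p1(1 − p1)/360], which is 4.3, 5.2 and 5.8 points at 95%, 90% and 85%. At 90% control use, an observed 10 points would carry an interval of roughly 4.8 to 15.2. These half-widths ignore provider clustering, for which the documents give no figure; positive within-provider correlation would generally widen them.

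**The case against.** The case for leaving the SAP as it is has real substance.

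- **Percentages are planned.** A reader might infer that the SAP reports this outcome only as an OR. It does not: arm percentages will be summarised, and a crude difference can be subtracted from them. This stands. What is missing is an interval for that difference and a statement of how the 10% is to be used.
- **The test is sound.** A reader might infer that the logistic GEE is invalid for a common outcome. OR = 1 and zero difference are the same null, and the robust errors are clustered by provider. No bias or error-rate problem follows. This stands in full.
- **Returning to the protocol's risk ratio would not settle the matter.** An RR of 8/9 is 10 points at 90% control use, but 0.95/9 = 10.6 points at 95% and 0.85/9 = 9.4 points at 85%. The preference for RR also depends on coding: as non-use, 20% v 10% is a risk ratio of 2.0 against an OR of 2.25. The protocol's model also carried a follow-up offset and more covariates, whereas the SAP says this outcome is not adjusted for disenrollment. The documents do not support requiring a switch of the primary estimate.
- **85–95% is not a forecast for the SAP's outcome.** The protocol anticipates 95% and treats the others as alternatives. Its figures refer to having an order at 6 months, while the SAP counts medication in hand at day 181 or at least 181 days' supply. This stands, but it does not rescue the OR: at assumed control use of 70% or 50%, ten points is OR 0.643 or 0.667, so the conversion still depends on the control percentage.
- **No interval comparison was promised.** The protocol says only that the difference was set so that clinical significance could be evaluated. This is true, but an evaluation without a measure of uncertainty is weak at the precision shown in step 5.
- **Timing.** The SAP was last updated in December 2021 and already describes age as differing between arms, so data had evidently been examined. That argues against replacing the primary estimate, but not against a labelled addition.

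**Conclusion.** The point holds as a gap in estimation and interpretation, not in testing. The only inferential estimate, interval and decision rule for Primary analysis I are on the OR scale. The protocol's criterion is 10%, best read as absolute points, and corresponds to OR 0.298, 0.444 or 0.529 across its three control rates. The OR interval cannot be read against that criterion, and the descriptive percentages come without an interval.

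The size of the mismatch rests on the protocol's control rates; the documents do not show what control use would be under the SAP's definition. That the criterion is in absolute points is inferred from the power table, since the text names no scale. The conclusion also holds if it is relative.

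**What to change.** Keep the logistic GEE as the primary test. Add to Primary analysis I:

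1. A marginal risk difference and risk ratio standardised from the same model. Predict each patient's probability of use with arm set to intervention and then to control, keeping the observed prior-hospitalization value. Average each set to obtain p1 and p0, and report p1 − p0 and p1/p0.
2. 95% CIs clustered by provider, by the delta method from the robust covariance matrix or by a provider-level bootstrap.
3. A sentence stating that the 10% minimal clinically important difference is in absolute points, and how the risk-difference interval is read against it: wholly beyond a 10-point reduction, spanning it, or wholly short of it.
4. The reason for departing from the Poisson model in protocol 8.2.1.

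If this change postdates access to unblinded data, label the risk difference and risk ratio as supplementary estimates.

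The cost is a few lines of code and one more reported estimate. The SAP already marks the outcome, arm and prior-hospitalization variables as present, and the primary test is unchanged.
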